### **Intra-patient comparison for ALA, AAR and annualized days of hemin use**

For patients who received placebo during the 6m-DB period and crossed over to receive givosiran during the OLE period, intra-patient comparisons for ALA, AAR and annualized days of hemin use will be performed to evaluate the efficacy of givosiran versus placebo.

For AAR and annualized days of hemin use, a negative binomial regression model with period as a main effect and patient as a random effect (PROC GENMOD with the REPEATED statement) will be fitted to compare the mean rate during the 6m-DB period while on placebo and that of the OLE period while on Givosiran treatment. In addition, individual patient’s AAR and annualized days of hemin use during the 6m-DB and the OLE periods will be calculated separately and compared graphically. To avoid an unstable estimation due to limited duration of follow-up, the

AAR and annualized days of hemin use will only be calculated for patients who have at least 85 days of follow-up during the OLE period.

For creatinine normalized ALA, Wilcoxon signed rank test will be used to make intra-patient comparisons on the medians over the 6m-DB period versus the OLE period, Month 3 vs. Month 9, and Month 6 vs. Month 12, when sufficient data are collected during the OLE period.

### **Treatment sequence**

Patients are assigned to receive either 2.5 mg/kg or 1.25 mg/kg once monthly dose of givosiran upon entry to the OLE period through the end of Month 12 (At Month 13, patients on 1.25 mg/kg once monthly dose may receive a dose adjustment). After sufficient data are collected during the OLE period, summaries for the All Givosiran Treated Set will be provided by the following subgroups:

- Givosiran/Givosiran:
  - Givosiran 2.5 mg/kg/Givosiran 2.5 mg/kg: all patients who received givosiran 2.5 mg/kg in 6m-DB and OLE periods.
  - Givosiran 2.5 mg/kg/ Givosiran 1.25 mg/kg: all patients who received givosiran 2.5 mg/kg in the 6m-DB period and givosiran 1.25 mg/kg in the OLE period;
  - Overall: all patients who received givosiran at any dose level in the 6m-DB, including patients who discontinued during 6m-DB and did not receive dose in OLE.
- Placebo/Givosiran:
  - Placebo/Givosiran 2.5 mg/kg: all patients who received placebo in the 6m-DB period and givosiran 2.5 mg/kg in the OLE period;
  - Placebo/ Givosiran 1.25 mg/kg: all patients who received placebo in the 6m-DB period and givosiran 1.25 mg/kg in the OLE period.
  - Overall: all patients who received placebo during the 6m-DB period and switched to givosiran at either dose level in the OLE period;
- Givosiran 2.5 mg/kg: all patients who received givosiran 2.5 mg/kg in either 6m-DB or OLE periods;
- All Givosiran: all patients who received any dose of givosiran during either 6m-DB or OLE period.

To assess the effect of givosiran 2.5 mg/kg and 1.25 mg/kg on ALA reduction separately, for the two subgroups Placebo/Givosiran 2.5 mg/kg and Placebo/Givosiran 1.25 mg/kg, Wilcoxon signed rank test will be conducted for intra-patient comparison on the medians over the 6m-DB period versus the OLE period, Month 3 vs. Month 9, and Month 6 vs. Month 12, when sufficient data are collected during the OLE period.

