6.2.2.2. During the Open-Label Extension Period (After Month 6 through End of Treatment)

Patients who crossed over to the OLE period prior to implementation of amendment 3 (ie, under amendment version 1 or 2) and are receiving 2.5 mg/kg once monthly will remain on that dose. Upon entry to the OLE period under amendment version 3, patients will cross over to receive a 1.25 mg/kg once monthly dose of givosiran. After implementation of amendment 3 and until implementation of amendment 5, a dose increase to 2.5 mg/kg once monthly may be permitted starting at Month 13 for patients receiving 1.25 mg/kg once monthly (see Section 6.2.3.4).

Upon implementation of amendment 5, all patients receiving 1.25 mg/kg givosiran once monthly who do not have ongoing clinically relevant transaminase elevations will have their dose increased to 2.5 mg/kg givosiran once monthly per guidance in Section 6.2.3.4.

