8.2.9. Other Analyses

The long-term efficacy and safety data of givosiran over the OLE period will be summarized descriptively. Patients who were randomized to placebo and received givosiran at a starting dose of 1.25 mg/kg once monthly during the OLE period (per amendment version 3) will be assessed to characterize the efficacy and safety for the lower dose 1.25 mg/kg once monthly.

Analyses for other exploratory endpoints such as exploratory biomarkers will be detailed in the SAP.

Additional data summaries to help understand any impact of the COVID-19 pandemic on efficacy and safety assessments will be performed, as appropriate.

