The start day of the OLE period is defined as the day when the first dose of the OLE period is administered. The assessments collected or AEs with onset after the administration of the first dose of the OLE period will be included in the OLE period. When assessments or AE onset dates are exactly the first OLE dose date with time missing, the records will be included in the OLE period.

- **During Givosiran Treatment**

For all patients who received at least one dose of givosiran, data will be summarized for the “during givosiran treatment” period, defined as below.

- 1) For patients who received givosiran in the 6m-DB period, all assessments collected after the first dose of givosiran during the entire study including both the 6m-DB and OLE periods (if available) will be included in the “during givosiran treatment”.
- 2) For patients who received placebo in the 6m-DB period and switched to givosiran in the OLE period, all assessments collected after the first dose of givosiran in the OLE period will be included in the “during givosiran treatment”.
- 3) For patients who discontinued givosiran treatment during the 6m-DB period, the data handling will follow the same rules as discussed above for “6m-DB period”. For discontinuation in the OLE period, assessments within 28 days of the last dose of givosiran will be included in summaries. For ongoing patients, all data are included.

Selected efficacy parameters will be summarized over the entire study including the 6m-DB and OLE periods for all patients to show the trajectory changes comparing the placebo experience versus the givosiran experience, for example, summary of creatinine normalized urinary ALA by visit. In these summaries, the treatment groups are “Givosiran” or “Placebo” based on randomization during the 6m-DB period.

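### SAP 5.10 sets no cut at a dose change, so the whole-OLE ALA comparison by dose and the by-dose summaries past Month 12 count 2.5 mg/kg data under 1.25 mg/kg (exploratory OLE only)

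*SAP*

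**What the plan says.** The Treatment sequence part of SAP 5.10 states its aim as "To assess the effect of givosiran 2.5 mg/kg and 1.25 mg/kg on ALA reduction separately". For the two placebo-crossover subgroups it specifies a Wilcoxon signed-rank "intra-patient comparison on the medians over the 6m-DB period versus the OLE period, Month 3 vs. Month 9, and Month 6 vs. Month 12", to be run once enough OLE data exist. Its lead-in says the OLE dose is assigned at entry and holds through Month 12, and adds: "At Month 13, patients on 1.25 mg/kg once monthly dose may receive a dose adjustment". SAP 2.1 makes clear that this adjustment is an increase to 2.5 mg/kg.

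The lower-dose subgroup is defined as "Placebo/ Givosiran 1.25 mg/kg: all patients who received placebo in the 6m-DB period and givosiran 1.25 mg/kg in the OLE period". Elsewhere in SAP 5.10, the OLE period starts at its first dose, and "AEs with onset after the administration of the first dose of the OLE period will be included in the OLE period". For placebo patients who cross over, "all assessments collected after the first dose of givosiran in the OLE period will be included" in the givosiran treatment period. The only stated cut is 28 days after the last dose for patients who discontinue in the OLE; ongoing patients contribute everything. SAP 5.8 uses all collected data at the hard lock.

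Protocol 8.2.9 characterizes the lower dose in placebo patients who "received givosiran at a starting dose of 1.25 mg/kg once monthly during the OLE period". Protocol 6.2.2.2 now goes beyond the optional Month 13 increase: on implementation of amendment 5, all patients on 1.25 mg/kg "who do not have ongoing clinically relevant transaminase elevations will have their dose increased to 2.5 mg/kg givosiran once monthly".

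**The concern.** An analysis meant to separate two doses has to say what happens when a patient moves from one to the other. SAP 5.10 foresees the move but gives no rule. Of its three by-dose ALA comparisons, the Month 3 versus 9 and Month 6 versus 12 tests end before the planned increase. The third, over the whole OLE, does not, and neither do cumulative by-dose summaries such as adverse-event incidence.

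The subgroup wording adds a smaller ambiguity. The lead-in points to the dose at OLE entry, but the bullets refer to the dose received. Read literally, a placebo patient increased during the OLE belongs to both the 1.25 and the 2.5 mg/kg crossover subgroups.

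At stake is the description of the 1.25 mg/kg dose that Protocol 8.2.9 asks for. If ALA is lower on 2.5 mg/kg, the apparent 1.25 mg/kg effect is pulled toward the higher dose, and late events on 2.5 mg/kg carry the wrong dose label.

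**Working it through.** **Extent of increases.** The rationale for protocol amendment 5 reports that investigators requested an increase for 14 of 37 patients on 1.25 mg/kg: 14/37 = 37.8%, which agrees with its 38%. These are requests, pooled over both former arms.

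**Scheduled OLE ALA samples (Protocol Tables 2 and 3).** Months 6.5, 7, 8, 9, 10, 11, 12 and 13 give 8; Months 14 to 18 give 5; Months 21, 24, 27, 30, 33 and 36 give 6. The total is 19. Samples are taken predose (Table 2, footnote j), so the sample at the visit of the increase still belongs to the old dose.

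**One patient.** Share of samples after the increase but counted under 1.25 mg/kg:

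| Increase at | Data to Month 18 | Data to Month 27 | Data to Month 36 |
|---|---|---|---|
| Month 13 | 5/13 = 38% | 8/16 = 50% | 11/19 = 58% |
| Month 18 | 0/13 | 3/16 = 19% | 6/19 = 32% |

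In time, a Month 13 increase (Day 365) with follow-up to Month 36 (Day 1009) puts (1009 − 365)/(1009 − 169) = 644/840 = 77% of OLE days after the increase. Because 11 of 19 is a majority, that patient's whole-OLE median falls on a 2.5 mg/kg value whenever ALA is lower on that dose. With data only to Month 12, 0 of 7 samples are affected.

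**A subgroup of 18 (assumed size).** 18 × 14/37 = 6.8, so take 7 increased at Month 13.

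- Other 11 never increased: 7×5/(18×13) = 35/234 = 15% of samples to Month 18; 7×8/(18×16) = 56/288 = 19% to Month 27; 7×11/(18×19) = 77/342 = 23% to Month 36.
- Other 11 increased at Month 18: (56 + 11×3)/288 = 89/288 = 31% to Month 27; (77 + 11×6)/342 = 143/342 = 42% to Month 36.

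**Shift in the descriptive effect.** SAP 9.1.2 gives planning values of 20.0 mmol/mol on placebo and 2.3 (SD 1.1) on 2.5 mg/kg. No level for 1.25 mg/kg is given, so 4, 6 and 8 were assumed. Without mixing, the reduction is 1 − 8/20 = 60% to 1 − 4/20 = 80%; on 2.5 mg/kg it would be 1 − 2.3/20 = 88.5%. A simulation (6,000 replicates; lognormal values around those levels; within-patient CV 30% or 50%) took the median across patients of each patient's OLE median, against 20.0, and compared it with the through-Month-12 result. Shifts in percentage points:

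| Scenario | To Month 18 | To Month 27 | To Month 36 | To Month 36, 48% between-patient spread |
|---|---|---|---|---|
| 7 increased only | 1.2–4.1 | 1.4–4.8 | 1.4–4.6 | 2.3–10.9 |
| Rest increased at Month 18 | – | 2.6–9.2 | 3.8–13.5 | 3.9–15.2 |

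The 48% is 1.1/2.3 from the SAP planning values.

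**The test itself.** With level 8, CV 50% and 48% spread, the signed-rank p-value against placebo was below 0.01 in all 600 mixed-dose runs. Mixing does not threaten that conclusion.

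**The case against.** The strongest reply is that the subgroups denote treatment sequences by OLE entry dose. Summarizing by starting regimen is legitimate, and Protocol 8.2.9 does so without a cut. That is a fair reading of the labels and it removes the overlap between subgroups. It does not rescue the stated aim of assessing each dose separately, because data on 2.5 mg/kg still enter the 1.25 mg/kg result.

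Second, much is already covered. Two of the three by-dose ALA tests precede Month 13, by-visit summaries keep the early values visible, and Protocol 1.4 bases its own dose comparison on the first 6 OLE months. This stands and limits the problem to one comparison and the cumulative or late by-dose summaries. An analysis run before anyone passes Month 13 would avoid it, but the SAP sets no such limit.

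Third, for the whole-OLE comparison the SAP names only a signed-rank test, whose p-value is safe; the shifts concern a descriptive size that it does not explicitly define. They also depend on inputs that the documents do not give. With an assumed 1.25 mg/kg level of 3 mmol/mol, the shift to Month 36 is only about 0.8 to 1.6 points. If the other 11 are increased at Month 24 rather than Month 18, the share is (77 + 11×4)/342 = 121/342 = 35% and the shift without between-patient spread about 3 to 10 points. These objections stand as limits on the size, not on the missing rule.

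Fourth, this SAP predates protocol amendment 5 and could not foresee the general increase. That is true, but it did know of the Month 13 increase, and the later change is a reason to update it.

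**Conclusion.** The concern holds and is minor. SAP 5.10 has no cut at a dose change, so the whole-OLE ALA comparison and by-dose summaries past Month 12 mix doses under the 1.25 mg/kg label. That part rests on the text and is firm, as are the sample counts, given full attendance at scheduled visits.

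The size of the ALA shift is illustrative. It depends on the assumed subgroup size, 1.25 mg/kg level, within-patient CV and timing of increases, and follow-up may end before Month 36. It ranges from about 1 point to about 15.

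Only exploratory OLE description is touched. The primary endpoint, the secondary endpoints and the alpha-controlled sequence are unaffected. So are the Month 3 versus 9 and Month 6 versus 12 tests with respect to the planned increase, provided groups follow OLE entry dose.

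**What to change.** In SAP 5.10:

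- State that the dose subgroups are by OLE starting dose, as in Protocol 8.2.9.
- Limit the by-dose 6m-DB versus OLE ALA comparison and the main by-dose summaries to data through Month 12, or to the first dose change if earlier, and report how many patients changed dose. The earlier-change clause also covers a different dose on rechallenge after an ALT hold (Protocol 6.2.3.1.1).
- Summarize later data of increased patients as a separate 1.25-to-2.5 mg/kg sequence, with events and exposure time attributed to the dose at onset.
- Label any 1.25 mg/kg summary past Month 12 that is cut at the increase as informatively censored.

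The cost is a few lines of SAP text and a dose-at-onset flag from existing dosing records; no new data are needed. The by-dose follow-up becomes shorter: 7 scheduled ALA samples per patient through Month 12 instead of up to 19. Any 1.25 mg/kg data kept beyond Month 12 and cut at the increase would lose the poorer responders, because increases before amendment 5 required an inadequate clinical response (Protocol 6.2.3.4).

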## **6. STATISTICAL ANALYSIS**

### **6.1. Patient Disposition**

Number and percentage of patients in the following categories will be summarized by treatment arm and overall as appropriate:

- Randomized
- Treated
- Completed the Months 3 and 6 visits
- Discontinued treatment and primary reasons for treatment discontinuation
- Withdrew from the study and primary reasons for withdrawal
- Entered the OLE period.

The number and percentage of patients enrolled by country and site will be summarized by randomized treatment arm and overall. The number and percentage of patients in each level of each randomization stratification factor recorded in IRS, and a comparison of the number and percentage of patients in each randomization stratification factor in IRS versus the clinical database will be summarized by randomized treatment arm and overall.

### **6.2. Demographics and Baseline Characteristics**

Demographic, background (e.g. medical history) and baseline disease characteristics will be summarized by treatment arm and overall.

Age, height, weight, and body mass index (BMI) will be summarized by descriptive statistics. Age group, sex, race, ethnicity, and region will be summarized by presenting the numbers and percentages of patients in each category.

The following baseline disease characteristics will also be summarized: age at diagnosis, time from diagnosis to randomization, prior hemin prophylaxis status (Y/N) at screening, number of attacks requiring hospitalization, urgent healthcare visits or IV hemin administration at home in the last 6 months prior to the study, prior chronic symptoms when not having attacks (Y/N) and prior chronic opioid medication usage when not having attacks (Y/N).

### **6.3. Protocol Deviations**

A protocol deviation is any change, divergence, or departure from the study design or procedures defined in the clinical protocol. Protocol deviations will be classified by medical review prior to primary analysis and major protocol deviations will be identified. A major protocol deviation is a deviation that may significantly impact the completeness, accuracy, and/or reliability of the trial data; that may significantly affect a subject's rights, safety, or well-being. (ICH. E3 R1 Structure and Contents of Clinical Study Reports Guidance for Industry. 2013) All major deviations related to trial inclusion or exclusion criteria, conduct of the trial, patient management or patient assessment will be described in the clinical study report.

The Sponsor or designee will be responsible for producing the final protocol deviation file (formatted as a Microsoft Excel file). This file will include a description of each protocol

deviation and whether or not this deviation is classified as a major protocol deviation. In addition, each major deviation will be clearly identified as to whether or not it warrants exclusion from the Per Protocol Set, based on the potential impact on the primary efficacy results according to the judgment of the Sponsor. This file will be finalized prior to study unblinding.

## 6.4. Drug Exposure

Exposure to study medication in days and the number of study drug SC administrations received will be summarized by treatment arm.

The last date of exposure to study drug is defined as the earliest day of the following dates:

- Last dose date + 27 days
- Analysis cutoff date
- The date of EOS

Duration of exposure is defined as the last date of exposure to study drug – date of the first dose +1. The exposure during the 6m-DB period is right censored by the date of the first OLE dose, i.e. the last exposure day in the 6m-DB period is no later than the day before the first OLE dose. Similarly, the exposure during the OLE is left censored by the date of the first OLE dose, i.e. the Day 1 of the OLE is the day of the first OLE dose.

Dose interruptions and compliance are not taken into account for duration of exposure.

## 6.5. Efficacy Analysis

All efficacy endpoints will be analyzed in both AIP and AHP patients. Model-based analysis for AIP and AHP patients will adjust for the two stratification factors, i.e. use of hemin prophylaxis at screening (Y/N) and historical AAR prior to randomization (High/Low), unless otherwise specified. For analysis of AHP patients, AHP type (AIP versus non-AIP) will not be included in the model due to the small number of non-AIP patients.

### Porphyria Attacks

Porphyria patients experiencing acute attacks present with highly morbid and potentially life-threatening symptoms relating to dysfunction across the central, peripheral, and autonomic nervous system. The most commonly seen signs and symptoms of a porphyria attack include diffuse, severe neurovisceral pain mostly in the abdomen, back, or limbs, nausea and vomiting, fatigue, hypertension, tachycardia, motor weakness.

Attacks can be reported by patients through eDiary or communicated with investigators. Protocol defined criteria for porphyria attacks include investigator-confirmed attacks requiring hospitalization, urgent healthcare visit, IV hemin administration at home, or treated at home not requiring hemin use. For data collection, each attack is reported with one associated outcome in the hierarchical order, e.g., if an attack requires both hospitalization and urgent healthcare, the attack will be reported as requiring hospitalization only. The porphyria attacks in the primary endpoint include those attacks requiring hospitalization, urgent healthcare visits or IV hemin administration at home.

The start time of a porphyria attack is defined as the time at which acute and sustained worsening of the patient's porphyria manifestations beyond normal day-to-day variability. The end of

porphyria attacks is characterized by recovery back to within a patient's normal day-to-day variability. Attacks that occur on the same calendar day of the last treated attack will be considered a part of the original attack and will count as one attack in the calculation of the AAR. Any attacks that begin on the next day from the last treated attack ends will constitute a new attack.

### 6.5.1. Primary Endpoint

The primary endpoint of the study is the annualized rate of porphyria attacks requiring hospitalization, urgent healthcare visit, or IV hemin administration at home in patients with AIP over the initial 6m-DB period. The primary analysis set for the primary endpoint is  $FAS_{AIP}$  (defined in Section 4).

The number of qualifying porphyria attacks is annualized for each patient using below formula:

$$\text{Annualized attack rate (AAR)} = \frac{\text{total number of porphyria attacks}}{\text{total number of days in the treatment period}} \times 365.25.$$

Let  $\lambda_G$  represent the mean AAR for givosiran arm and  $\lambda_O$  represent the mean AAR for the placebo arm. The hypotheses of the primary analysis are:

$$H_0: \frac{\lambda_G}{\lambda_O} = 1 \quad H_A: \frac{\lambda_G}{\lambda_O} \neq 1$$

The statistical significance level for the primary analysis of the primary endpoint is 2-sided 0.049. An estimated AAR ratio :  $\frac{\lambda_G}{\lambda_O} < 1$  and 2-sided p-value  $< 0.049$  will lead to rejection of  $H_0$ .

#### 6.5.1.1. Primary Analysis using Negative Binomial Regression Model

The primary analysis will be performed using a negative binomial regression model that include fixed effects of the treatment arms, the stratification factors for the AIP patients, which include the hemin prophylaxis regimen prior to the study (yes vs no) and historical AAR (high vs low). The logarithm of the amount of time (in the units of year) that each patient spends in the 6m-DB period will be included in the model as an offset variable. With the offset variable, the negative binomial regression model essentially models the AAR for each patient based on the length of time in the treatment period, and hence will be able to account for the different lengths of follow-up time.

For patients who discontinue the study treatment early (before the end of the 6m-DB period), best efforts will be made to continue the collection of attack and hemin use data. The primary efficacy analysis will be based on all qualified attacks occurring in the 6m-DB period, including those that occur after treatment discontinuation. No imputation of attack data is planned for the primary analysis.

In addition to p-value, an estimated ratio of mean AARs between the two treatment arms with the corresponding 95% confidence interval will be estimated from the negative binomial regression model. Descriptive statistics for the median and interquartile range of the annualized attack rate will also be presented by treatment arm.

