## 5. GENERAL STATISTICAL METHODS

### 5.1. Determination of Sample Size

The planned total enrollment for the study is approximately 74 patients, including approximately 70 AIP patients.

Seventy patients will yield at least 90% power to detect a 45% reduction in the annualized attack rate at a 2-sided 5% significance level assuming a mean annualized attack rate of 8, a standard deviation (SD) of 5 in the placebo arm (mean/SD of 4/2.9 for 6 months to preserve the over-dispersion of 3.8), and a mean annualized attack rate of 4.4 with SD of 3 in the givosiran arm (mean/SD of 2.2/1.8 for 6 months to preserve the over-dispersion of 4.2), using a negative binomial model. This study design will still have at least 80% power even if the dropout rate is as high as 15% under the same assumptions.

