## 5.5. Randomization Stratification Factors

Randomization for this study is first stratified by AHP type: AIP [with genetic evidence of a mutation in the *HMBS* gene] vs non-AIP [HCP, VP, ADP, or any AHP without an identified mutation in a porphyria-related gene].

The AIP patient stratum is further stratified by the use of hemin prophylaxis or not immediately prior to Screening, and on the historical AAR. Patients who had been on hemin prophylaxis will be stratified by their historical AAR of  $<7$  vs  $\geq 7$ . Patients who had not been on a hemin prophylaxis will be stratified by their historical AAR:  $<12$  vs  $\geq 12$ . This historical AAR is calculated based on the medical record reviewed for inclusion criterion of at least 2 attacks requiring hospitalization, urgent healthcare visit or IV hemin administration at home within the 6 months prior to randomization.

Since only a few patients in the non-AIP stratum of HCP, VP, ADP, or any AHP without identified mutation in a porphyria-related gene are anticipated to be enrolled in the study, there is no further stratification within the stratum.

The historical AAR prior to randomization will be classified into high versus low when used as a categorical covariate. For patients on a hemin prophylaxis regimen at the time of screening, high attack rate is defined as  $AAR \geq 7$ . For patients not on a hemin prophylaxis regimen at screening,  $AAR \geq 12$  is considered as high attack rates.

Stratification factors are recorded in both the IRS and the clinical database. In statistical analyses that use randomization stratification factors as covariates, the stratum assignment will reflect the values as recorded in the clinical database. In the presence of stratification errors, the stratification used in analysis may not match that in the IRS. In addition, for non-AIP patients, the two AIP-specific stratification factors hemin prophylaxis regimen and historical AAR are collected in the clinical database and will be used as covariates in the analysis of AHP population.

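### The primary model uses the historical attack rate only as high/low; adding its logarithm beside the strata factors is a cheap refinement that could trim the standard error by about 0–5%

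*SAP*

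**What the plan says.** SAP Section 6.5.1.1 specifies a negative binomial model with treatment arm, prior hemin prophylaxis (yes/no) and "historical AAR (high vs low"), with log follow-up time as offset. SAP Section 5.5 gives the rule: "The historical AAR prior to randomization will be classified into high versus low when used as a categorical covariate". The cut is 7 for patients on prophylaxis at screening and 12 for the others. SAP Section 6.5 carries the same two factors into the model-based efficacy analyses generally. None of the sensitivity analyses in SAP Section 6.5.1.4 uses the numeric rate.

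The number exists. SAP Section 5.5 says that the factors are recorded in the clinical database, for non-AIP patients too. SAP Section 6.2 lists among the baseline summaries the "number of attacks requiring hospitalization, urgent healthcare visits or IV hemin administration at home in the last 6 months prior to the study".

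Elsewhere the SAP does use baseline as a continuous covariate: for ALA and PBG and for SF-12 PCS (Section 6.5.2), and for ALA at the interim analysis (Section 9.1.3.1).

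**The concern.** The historical count is a baseline measurement of the same kind of event as the primary outcome. Reducing it to one cut discards differences between patients on the same side of that cut.

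Eligibility requires at least 2 qualifying attacks in 6 months (Protocol Section 5.1), which is 4 a year if doubled. Without prophylaxis, 'low' therefore covers 2 to 5 attacks in 6 months (4 to 10 a year), and 'high' has no upper limit. With prophylaxis, 'low' holds only counts of 2 and 3.

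At stake is some precision in a comparison of about 70 patients with over-dispersed counts. Validity and type I error are not in question.

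**Working it through.** **1. The plan's power.** SAP Section 5.1 states: "Seventy patients will yield at least 90% power to detect a 45% reduction in the annualized attack rate at a 2-sided 5% significance level". For placebo it takes 8 attacks a year, with "a standard deviation (SD) of 5 in the placebo arm (mean/SD of 4/2.9 for 6 months to preserve the over-dispersion of 3.8"). The givosiran inputs are 4.4 attacks a year (SD 3), scaled to 2.2 (SD 1.8) over six months, and an over-dispersion of 4.2.

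- Shape k = mean²/(variance − mean), from the annual figures: placebo 64/(25 − 8) = 3.76; givosiran 19.36/(9 − 4.4) = 4.21. These match the stated 3.8 and 4.2.
- SE of log rate ratio = √[(1/4 + 1/3.76 + 1/2.2 + 1/4.21)/35] = √(1.208/35) = 0.186.
- |ln 0.55|/0.186 = 0.598/0.186 = 3.22. Power = Φ(3.22 − 1.96) = 89.6% at 0.05, and 89.4% at 0.049. Using a pooled or reference-arm null variance gives 90.4% or 92.0% at 0.05.
- With 15% dropout (29.75 per arm), SE = 0.2015 and power = 84.3%. The SAP says "This study design will still have at least 80% power even if the dropout rate is as high as 15" per cent.

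The plan's figure is reproduced.

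**2. Is there heterogeneity to explain?** The six-month placebo variance is 2.9² = 8.41. Poisson noise accounts for 4, leaving 4.41, about 52%, as between-patient variation. How much of that history explains is not stated in the documents.

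**3. Simulated gain.** Trials of 70 patients were simulated with a rate ratio of 0.55, stratified randomization and the eligibility minimum of 2 attacks in 6 months (4,000 trials per base scenario, 2,500 per variant). Each patient's historical and on-study underlying rates are log-normal with correlation ρ. Assumptions not in the documents:

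- ρ from 0 to 1;
- 40% on prior prophylaxis (varied 20–60%);
- mean historical rates of 7 and 12 a year (varied to 8 and 8);
- common k = 4 (varied to 2 and 1).

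The table shows the mean reduction in the model SE when log(historical AAR) is added to the SAP model, at k = 4.

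| ρ | 6-month history | 12-month history |
|---|---|---|
| 0 | −0.1% | — |
| 0.3 | 0.2% | 0.3% |
| 0.5 | 0.8% | 1.1% |
| 0.7 | 1.9% | 2.5% |
| 0.85 | 3.1% | 4.1% |
| 1.0 | 4.8% | 6.3% |

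For example, with 12 months and ρ = 0.85 the SE goes from 0.1689 to 0.1620, and 1 − 0.1620/0.1689 = 4.1%.

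**4. In patients.** An SE reduction r is worth 1/(1 − r)² − 1 extra patients. For r = 1.9%, 3.1% and 4.8% this is 3.9%, 6.5% and 10.3%, or about 3, 5 and 7 of 70.

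**5. In power (α = 0.049, 6-month history, base scenario).** Power goes from 91.5% to 91.8% at ρ = 0.5, from 92.5% to 93.3% at 0.7, and from 94.2% to 95.7% at 1.0. Some variants at k = 4 and ρ = 1 gained up to 2.2 points. With 12 months and ρ = 0.3, power stayed at 91.6%.

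**6. Sensitivity.** Varying the prophylaxis share or the mean historical rates moved the six-month gain at ρ = 1 only between 3.9% and 5.2%. More dispersion than planned raises it. At ρ = 0.5, 0.7, 0.85 and 1.0, k = 2 gives 1.4%, 3.2%, 6.0% and 11.2%, and k = 1 gives 1.7%, 4.4%, 8.8% and 19.3%.

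**The case against.** The planned model is sound. It follows Protocol Section 8.2.5.1, which names treatment and the stratification factors, and adjusting for those factors as randomized is standard. Nothing in it is biased or contradictory. The stratified simulations already give about 91–94% power in the base scenarios, so the added covariate rescues nothing.

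The benefit also rests on an unknown correlation, and there are reasons to expect less than a perfect one:

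- Patients must stop prophylactic hemin at screening (Protocol Section 5.1), so history in that group was accrued under a different regimen.
- A single log slope assumes the same relation with and without prior prophylaxis, although the plan uses different cuts for the two groups.
- The larger figures need a twelve-month count. Protocol Section 4.4 speaks of the past 12 months, but SAP Section 5.5 derives the rate from the six-month eligibility record, and SAP Section 6.2 summarizes a six-month count.

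All of this stands. It limits the size of the gain and makes the change optional. It does not remove the case, because the worst simulated loss at the planned dispersion was 0.1% of the SE. With a log link and a constant rate ratio, the larger model also estimates the same treatment effect.

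**Conclusion.** This is a small, optional efficiency gain and not an error in the plan. At the planned dispersion, the SE of the log rate ratio falls by about 0–5% with the SAP's six-month history and by about 0–6% with twelve months. A fall of 2% or more with the six-month history needs ρ of about 0.7 or higher. Base-case power rises by about 0–1.5 points.

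A reader might infer more than the documents support:

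- **A dependable gain of 2–7%.** The documents give no correlation. A 7% fall appears at the planned dispersion only in the empirical SD, at ρ = 1 with a twelve-month history (0.1712 to 0.1592).
- **That an SD of 5 around a mean of 8 shows the spread within 'low' and 'high'.** SAP Section 5.1 gives these as the overall on-study figures for placebo. They include Poisson noise (8 of the variance of 25) and say nothing about spread within strata.
- **That history is the strongest baseline predictor.** This is plausible, but no passage shows it.
- **That the hemin-days model should change too.** Attack history is not baseline hemin use, and no gain was computed for that model.

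**What to change.** Before unblinding:

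1. Settle the history window, 6 months (SAP Section 5.5) or 12 months (Protocol Section 4.4), and use it consistently.
2. In SAP Section 6.5.1.1, and in the matching AHP attack-rate model in Section 6.5.2, add log(historical AAR) as a continuous covariate and keep both stratification factors.
3. State a rule for a historical count of zero. Eligibility should prevent one, but the full analysis sets include every randomized and dosed patient, so one enrolled in deviation would have an undefined logarithm.
4. Keep the present two-factor model as a named sensitivity analysis.

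The cost is a few lines of SAP text, one parameter and a log-linear assumption. With the six-month window no new data are needed. If the primary model cannot be reopened, pre-specify the extended model as a sensitivity analysis instead. SAP Section 1 places sign-off of Amendment 2 before unblinding, so that was the natural point for the change. After unblinding, the two-factor model should stand as primary and this analysis should be labelled post hoc.
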